STUDY PROTOCOL

Title:

Effectiveness of Photobiomodulation, Er:YAG Laser Therapy, and Clobetasol in the Treatment of the Erosive Form of Oral Lichen Planus: A Randomized Clinical Trial

Planned Study Period:

December 1, 2025 to December 1, 2027

The study will begin after approval from the Bioethics Committee.

I. STUDY OVERVIEW

Objective

The aim of this study is to evaluate and compare the therapeutic effectiveness of photobiomodulation (PBM), Er:YAG laser therapy, and topical clobetasol in the treatment of the erosive form of oral lichen planus (OLP). The study focuses on:

1. Healing rate of erosive lesions.
2. Reduction of pain intensity.
3. Improvement of oral function, including chewing, swallowing, and tolerance of removable prosthetic appliances.
4. Comparison of recurrence rates after treatment.

Rationale and Originality

Oral lichen planus is a chronic inflammatory disease of the oral mucosa, often associated with pain and impaired function, especially in the erosive variant. Topical corticosteroids, such as clobetasol, remain the standard of care, but long term use is limited by adverse effects and frequent relapses. Alternative therapies, including PBM and laser based treatments, have gained attention due to their potential benefits and improved safety profile. Evidence for the use of surgical or ablative lasers in erosive OLP remains limited and inconsistent. This study will directly compare three therapeutic modalities and provide clinically valuable information to support more effective and safer treatment strategies.

II. MATERIALS AND METHODS

Study Design

Randomized controlled clinical trial with three parallel arms.

Study Population

A total of 60 participants (male and female) aged 20 years or older will be recruited from the Clinic of Conservative Dentistry and Periodontal Diseases at the University Center of Dentistry, Medical University of Silesia in Zabrze, Poland.

Study Groups

Participants will be randomly assigned into three equal groups:

1. **Group 1:** Photobiomodulation (PBM)
2. **Group 2:** Er:YAG laser therapy
3. **Group 3:** Topical clobetasol (control)

Inclusion Criteria

- Age 20 to 70 years.
- Histopathological confirmation of erosive or ulcerative OLP.
- Absence of aerobic bacterial or fungal infection of the oral cavity.
- No OLP treatment within the past 3 months.
- Written informed consent.

Exclusion Criteria

- Systemic diseases or conditions including uncontrolled diabetes (random glucose ≥ 200 mg/dl), cardiovascular failure, pacemaker implantation, connective tissue diseases (such as lupus with positive ANA1 or ANA2).
- Current or past malignant disease.
- Graft versus host disease.
- Hematologic disorders including anemia, leukemia, lymphoma, bleeding disorders, hemophilia A, B, or C, and von Willebrand disease.
- G6PD deficiency, porphyria.
- Hepatitis A, B, or C.
- Vaccination within the past 6 months.
- Use of medications associated with lichenoid reactions, including beta blockers, diuretics, ACE inhibitors, methyldopa, sulfonylureas, lithium, gold salts, arsenic compounds, mercury, ibuprofen, tetracyclines, and sulfonamides.
- Pregnancy or breastfeeding, including up to 6 months post lactation.
- UV light hypersensitivity.
- Smoking more than 5 cigarettes per day.
- Lesions adjacent to amalgam fillings or metal prosthetic restorations.
- Presence of dysplastic changes of any grade.
- OLP treatment within 3 months prior to enrollment.
- Active fungal or bacterial infection.
- Lack of consent to participate.

Interventions

Group 1: Photobiomodulation (PBM)

- Diode laser 635 nm, power 100 mW, continuous mode, fluence 4 J/cm².
- Power density 0.2 W/cm².
- Exposure time 15 seconds per point.
- 8 mm flat glass fiber, spot size 0.5 cm², Gaussian energy distribution.
- Noncontact application at approximately 1 mm from the lesion.
- Sessions twice weekly until complete healing, maximum 8 sessions.

Group 2: Er:YAG Laser Therapy

- Pulse energy 80 mJ, frequency 10 Hz, power 0.8 W.
- Pulse duration 300 μ s.
- Water cooling 5 and air cooling 5.
- 0.06 mm flat fiber, noncontact, 3 mm from lesion surface.
- Sessions once weekly until healing, maximum 4 sessions.

Group 3: Topical Clobetasol

- Clobetasol propionate 0.05 percent ointment.
- Applied to clean, dry mucosa twice daily for 30 days.

Pre Treatment Examinations

- Mycological and bacteriological swabs from both cheeks and posterior pharyngeal wall.
- Autofluorescence evaluation using a 405 nm diode laser to guide biopsy site selection.
- Histopathological analysis of a biopsy sample from the lesion.

III. CLINICAL ASSESSMENT

Assessment Schedule

- Baseline before treatment.
- One week after final session or cessation of steroid application.
- One month after treatment.
- Three months after treatment.

Clinical Parameters

- Lesion size in mm^2 , including erosions, atrophic areas, and white lesions.
- Thonprasom scale grading from 0 to 5.
- Lesion size measured using transparent millimeter grid foil.

Scoring System

- R: reticular score
- A: atrophic score
- E: erosive or ulcerative score

Formula:

$$\text{REA} = (R \times 1) + (A \times 1.5) + (E \times 2)$$

Efficacy Index (EI)

$$\text{EI} = [(\text{baseline REA score} - \text{post treatment REA score}) \div \text{baseline REA score}] \times 100 \text{ percent.}$$

Interpretation:

- 100 percent: complete healing
- 75 to <100 percent: significant improvement

- 25 to <75 percent: moderate improvement
- 0 to 25 percent: slight improvement
- 0 percent: no improvement

Subjective Assessments

- Pain: Visual Analogue Scale (0 to 10).
- Swelling or discomfort: numeric scale (0 to 10).

Symptom Improvement (N)

$N = [(baseline score - post treatment score) \div baseline score] \times 100$ percent.

Recurrence Evaluation

Follow up at 1 week, 1 month, and 3 months after treatment.

Mycological Testing

Performed before and after treatment to identify *Candida* colonization and secondary fungal infection.

IV. ETHICAL CONSIDERATIONS

The study will be conducted according to the Declaration of Helsinki. Ethics approval and written informed consent will be obtained before enrollment.

V. EXPECTED OUTCOMES

The study aims to identify the most effective treatment modality for erosive OLP, improving patient quality of life and reducing recurrence.

VI. POTENTIAL RISKS

Risks may include redness, swelling, pain, burning sensation, or changes in pigmentation. Rare risks include allergic reactions, photosensitivity, ulceration, or worsening of mucosal lesions.

VII. BENEFITS TO PARTICIPANTS

PBM and Er:YAG laser therapy may accelerate healing, reduce pain, support oral function, and offer a safer alternative to long term corticosteroid therapy. Laser procedures are noncontact and selective, minimizing injury to healthy tissue and promoting faster recovery.

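### The protocol aims to name the most effective of three treatments but fixes no primary outcome and no primary visit, so the headline can be chosen after the results

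*Protocol*

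**What the plan says.** Section I (Objective) introduces four aims with the words "The study focuses on". The first listed is about lesions closing ("Healing rate of erosive lesions"). The second is pain relief. The third is oral function, covering eating and the wearing of dentures. The last is relapse, worded as "Comparison of recurrence rates after treatment". The list is numbered, but nothing says that the numbers are an order of priority.

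Section II (Study Design) describes a "Randomized controlled clinical trial with three parallel arms", with 60 participants in three equal groups, so 20 per arm.

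Section III sets three post-treatment assessments. The first is "One week after final session or cessation of steroid application"; the others are at one month and three months after treatment. The section lists five measures of effect: lesion size, the 0 to 5 clinical grade, the REA score with its Efficacy Index, pain on a visual analogue scale, and a numeric scale for swelling or discomfort.

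Section V gives the conclusion sought: "The study aims to identify the most effective treatment modality for erosive OLP". No section says which objective, measure or visit decides it.

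**The concern.** A trial that sets out to name a best treatment has to say what best means. The outcome and the time point define that question and belong in the protocol. How they are tested can be left to an analysis plan.

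Two things are at stake. First, the measures need not agree, so the choice of measure can change which arm is favoured. Second, if the treatments are equally effective, having many outcomes and visits to choose from raises the chance that some comparison looks significant and becomes the headline.

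**Working it through.** The protocol gives no alpha, power or sample-size derivation, so there is no stated figure to reproduce.

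**Can the measures disagree?** Section III defines REA = R × 1 + A × 1.5 + E × 2, and EI as the percentage fall in REA. As an illustration with assumed values, let a patient start with E = s and R = A = 0, and let the erosion become a reticular lesion of the same area with R = s.

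- Erosive score: from s to 0, complete resolution.
- Efficacy Index: (2s − s) ÷ 2s = 50 percent, which section III calls moderate improvement.
- Total lesion area, which counts erosions, atrophic areas and white lesions: no change.

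The same course gives three different readings within objective 1 alone.

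**How many comparisons are open?** Three arms give 3 pairs, and there are 3 post-treatment visits.

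- Healing and pain at each visit, recurrence as one rate, oral function dropped: 2 × 3 × 3 + 3 = 21.
- Healing, pain and recurrence at each visit: 3 × 3 × 3 = 27.
- All four objectives at each visit: 4 × 3 × 3 = 36.
- The five scheduled measures at each visit: 5 × 3 × 3 = 45, or 54 with recurrence as a sixth.

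**Chance of at least one false positive.** Independent tests would give 1 − 0.95^k, which is 0.842 for k = 36. These tests share arms, patients and visits, so independence does not hold. A simulation was used instead: no true difference, 20 per arm, normal outcomes, pairwise t-tests at two-sided 5 percent, assumed correlations between outcomes and between visits, 20,000 runs per setting. Each cell gives the percentage for unadjusted pairs, then for pairs tested only after a significant global F-test at that outcome and visit.

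| Correlation (outcomes / visits) | 21 tests | 27 tests | 36 tests |
|---|---|---|---|
| 0.3 / 0.5 | 54, 27 | 62, 32 | 72, 40 |
| 0.5 / 0.7 | 46, 23 | 53, 27 | 60, 32 |
| 0.7 / 0.8 | 38, 18 | 42, 21 | 50, 26 |
| 0.9 / 0.9 | 28, 13 | 30, 14 | 33, 16 |

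With 45 tests the figures are higher: 78 and 47 percent at 0.3 / 0.5, and 36 and 17 percent at 0.9 / 0.9.

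**With one outcome at one visit.** Three unadjusted pairs give about 12 percent. A global test followed by pairs gives about 5 percent.

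**The case against.** The strongest reply is that the protocol states no test, no alpha and no unadjusted pairwise testing, and that an analysis plan may exist. Part of the inflation does come from an assumed testing rule: with a global test first, 72 percent falls to 40 percent in the least correlated case shown. The correlations and normality are also assumed, while the clinical grade is ordinal and healing or recurrence may be binary. All this stands, and it is why the size is given as a range. A missing multiplicity adjustment is therefore not charged to this protocol.

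A reader might also infer more than the document supports:

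- *That there are at least 36 comparisons.* Oral function has no instrument in section III, and recurrence may be a single rate, so 36 is one possible count and not a minimum.
- *That the false-positive risk is 84 percent.* That figure needs independent, unadjusted tests at 5 percent. The protocol states none of this, and measurements on the same patients are not independent.
- *That a false winner would usually appear.* Under higher correlation the chance is half or less.
- *That leading on any measure at any visit meets the aim.* The protocol gives no deciding rule at all, so it does not give that one.

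It can further be said that healing is listed first, and that the Efficacy Index is the one clinical measure named for efficacy and given response categories. Neither is labelled primary, and the index is computed at no designated visit. The gap remains.

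**Conclusion.** The point holds in this form: the protocol promises to name a best treatment but fixes neither the outcome nor the visit that decides it. This can be seen from the document alone and does not depend on any count. Measures within one objective can give different readings of the same patient, and the headline can be chosen once the results are known.

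The size is approximate. For 21 to 36 comparisons with 20 per arm, the chance of at least one false winner is roughly 30 to 70 percent without adjustment, and about 13 to 40 percent with a global test first at each outcome and visit. Both ranges rest on assumed two-sided 5 percent tests, normal outcomes and correlations from 0.3 / 0.5 to 0.9 / 0.9. Even the lowest figure is more than twice 5 percent, so the conclusion survives the more lenient testing rule.

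**What to change.** In section I, name objective 1 (healing of erosive lesions) as primary. Define it by one measure already collected, for example the erosive score E with its scale stated, since section III gives none. If healing rate is meant as a proportion healed or a time to healing, say so. Fix one of the three scheduled visits, for example one month after treatment, before any outcome data are seen. Make all other measures and visits secondary, and state in section V that the choice of most effective treatment rests on the primary outcome only.

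The testing rule can be set in the analysis plan. A global three-arm test at 5 percent, followed by pairs at 5 percent only if it is significant, adjusted for the baseline value, would hold the overall error near 5 percent. With three arms this is a closed procedure: if only two arms are equal, only one pairwise null hypothesis is true.

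The cost is a few sentences, with no change to treatment, visits or data collection. The downside is that pain, function and recurrence become supportive. Naming a primary outcome also does not add power. With 20 per arm, a normal approximation puts the difference detectable with 80 percent power in one pair at (1.960 + 0.842) × √(2/20) = 0.886 standard deviations, before any gain from baseline adjustment.

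### Oral function is one of the four objectives, but no listed assessment measures chewing, swallowing or appliance tolerance

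*Protocol*

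**What the plan says.** Section I (Objective) of the Protocol numbers four things on which the study focuses: healing rate, pain, oral function and recurrence. The third reads: "Improvement of oral function, including chewing, swallowing, and tolerance of removable prosthetic appliances".

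Function appears in two other places. The rationale in Section I describes the disease as "often associated with pain and impaired function, especially in the erosive variant". Section VII says that the two laser treatments "may accelerate healing, reduce pain, support oral function". Neither place attaches a measure.

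What is measured is set out in Sections II and III. Before treatment there are "Mycological and bacteriological swabs from both cheeks and posterior pharyngeal wall", an autofluorescence examination and a biopsy. Section III then gives one baseline visit and three follow-up visits, the first being "One week after final session or cessation of steroid application". Its clinical parameters are lesion size ("including erosions, atrophic areas, and white lesions") and the "Thonprasom scale grading from 0 to 5", followed by the REA score and its Efficacy Index. The subjective assessments are a pain VAS and one further item: "Swelling or discomfort: numeric scale (0 to 10". Section III ends with a percentage symptom-improvement formula (N), the recurrence visits and mycological testing.

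**The concern.** A numbered objective with three named components should have at least one assessment able to answer it. Here the healing and pain objectives have explicit instruments and the function objective has none.

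Two outcomes are likely if this is left alone. The final report may drop the objective without comment, or the swelling-or-discomfort score may be presented as evidence on function. The second is the more harmful. That score could fall because swelling subsided while the patient ate no better and tolerated a denture no better, and a between-arm difference in it would then be misread as a functional benefit.

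This is not a detail that a protocol can leave to the SAP. An SAP decides how collected data are analysed. It cannot supply baseline ratings that nobody was asked to collect.

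**Working it through.** The plan gives no figure to reproduce, so the check is a match of objectives to assessments.

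| Objective (Section I) | Assessments in Section III that address it |
|---|---|
| 1. Healing of erosive lesions | Lesion size, Thonprasom grade, REA and Efficacy Index |
| 2. Pain | VAS, 0 to 10 |
| 3. Oral function: chewing | None named |
| 3. Oral function: swallowing | None named |
| 3. Oral function: appliance tolerance | None named |
| 4. Recurrence | Follow-up visits at 1 week, 1 month and 3 months |

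The items not in the table do not fill the gap. The swabs, autofluorescence and biopsy are pre-treatment examinations, and mycology concerns *Candida*. N is a percentage change computed from a baseline and a post-treatment score, so it adds no new measurement.

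Two items might be offered as substitutes.

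- **Swelling or discomfort.** The scale type and range are stated. Its content is not: two symptoms are joined by an *or*, there are no anchors or recall period, and the activity during which discomfort is rated is not given. A change in the score cannot be attributed to chewing, swallowing or appliance wear.
- **Pain VAS.** The Protocol treats pain and function as distinct in three places: as separate objectives in Section I, as separate terms in the rationale, and as separate benefits in Section VII. On the document's own terms, the pain score is not a function measure.

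**Result:** 0 of 3 named components of objective 3 is matched to a listed assessment.

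**Appliance component.** Wearing a removable appliance is not an inclusion criterion, and appliance wear is not listed as recorded. The number of participants to whom this component applies, *w*, is therefore unknown. The exclusion of lesions next to metal prosthetic restorations may lower it.

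**Workload of the remedy** (this is not the size of the defect). With 2 items for everyone, 1 further item for wearers, 4 visits, 60 participants and full follow-up:

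ratings = (2 × 4 × 60) + (1 × 4 × *w*) = 480 + 4*w*

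| Assumed *w* | Ratings |
|---|---|
| 0 | 480 |
| 20 | 480 + 80 = 560 |
| 60 | 480 + 240 = 720 |

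Per participant this is 2 × 4 = 8 ratings, or 3 × 4 = 12 for a wearer.

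**The case against.** The best defence is that Section III is a short list that does not claim to be exhaustive. The case report forms are not shown, so function may be recorded even though the Protocol does not name it. Discomfort could also be meant to include discomfort on eating, and the item does have a stated 0 to 10 range with a change formula that follows it.

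Part of this stands. The Protocol shows that no function rating is *named*; it does not prove that none will be taken. The swelling-or-discomfort item is also not wholly undefined, since only its content is left open. But if a function item exists on a form, the Protocol should name it, which is a one-line correction. If discomfort on eating is intended, the item must say so, and it would still be merged with swelling and silent on appliances.

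It is also fair to say that a scheduled visit is not the same as a measure, and that for recurrence Section III gives only visit times. This point therefore makes no claim that the other objectives are fully specified. It says only that the present gap does not touch them.

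Finally, the start was planned for December 1, 2025, and the Protocol cannot show whether enrolment has begun. That affects how the remedy is applied, not whether the gap exists.

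**Conclusion.** The concern holds. Objective 3 names three components and no listed assessment covers any of them, so a trial run as written would have no direct baseline or follow-up data on that objective. One of four objectives is affected. The gap does not bear on participant safety or on the lesion and pain comparisons, and the Protocol does not rank any objective as primary, so this should be corrected but does not undermine the trial as a whole.

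The conclusion rests on one assumption: that the assessments named in Sections II and III are the ones that will be carried out. It does not depend on the number of appliance wearers, which affects only the workload of the remedy and how much can be said about appliance tolerance.

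**What to change.** Before enrolment, do one of the following.

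1. **Add a measure.** Name a patient-rated function measure covering chewing and swallowing, for example two 0 to 10 items with stated anchors and recall period, at baseline and at the three existing follow-up visits. Record removable-appliance wear (yes or no) at baseline. Rate appliance tolerance in wearers only and report it descriptively, because that subset is of unknown size and may be small.
2. **Remove objective 3** and make no claim about function in the report.

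If participants have already been enrolled, their baseline function cannot be recovered. Introduce the items as early as possible, report by arm how many participants lack a baseline rating, and limit change-from-baseline summaries to those who have one.

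The first option needs a short amendment, with ethics review of the changed protocol, and no extra visits or procedures. The burden is the 480 to 720 ratings shown above. Its weakness is that the Protocol gives no evidence for the validity of simple 0 to 10 function items, so results on function should be labelled supportive. The second option costs almost nothing but gives up the aim.

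### The photobiomodulation settings in Group 1 deliver 3 J/cm², not the 4 J/cm² that the protocol states

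*Protocol*

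**What the plan says.** Section II of the protocol, under Interventions, Group 1, lists the PBM settings line by line:

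- power, mode and dose: "Diode laser 635 nm, power 100 mW, continuous mode, fluence 4 J/cm²"
- irradiance: "Power density 0.2 W/cm²"
- time: "Exposure time 15 seconds per point"
- optics: "8 mm flat glass fiber, spot size 0.5 cm², Gaussian energy distribution"
- distance: "Noncontact application at approximately 1 mm from the lesion"
- schedule: "Sessions twice weekly until complete healing, maximum 8 sessions"

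The protocol mentions no second pass over a point and no overlap of points. It does not describe the 4 J/cm² as a peak or cumulative value.

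**The concern.** Once power, spot area and exposure time are fixed for a continuous beam, the fluence follows from them and cannot be chosen separately. The protocol fixes all three and also states a fluence, and that fluence is not the one they produce.

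The list defines the treatment in one of the three randomised arms. If some sessions are run by the clock and others by the fluence figure, the arm contains two doses. If every session is run at 15 s but reported at 4 J/cm², the report misstates what patients received, and neither an effect nor a lack of effect could be attributed to the stated fluence. Analysis cannot repair this afterwards, because it concerns the energy physically delivered.

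**Working it through.** **Inputs**, all from the Group 1 list: power P = 100 mW = 0.1 W, continuous; spot area A = 0.5 cm²; fibre 8 mm; power density I = 0.2 W/cm²; time t = 15 s per point; stated fluence F = 4 J/cm².

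**Step 1: do the optical figures agree with each other?**
- P / A = 0.1 / 0.5 = 0.2 W/cm², exactly as stated.
- An 8 mm diameter gives π × (0.4 cm)² = 0.503 cm², which rounds to the stated 0.5 cm².

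Power, spot, fibre and power density therefore form a consistent set.

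**Step 2: the fluence they deliver.** A continuous beam has no duty-cycle factor.
- F = I × t = 0.2 × 15 = 3.0 J/cm².
- F = P × t / A = 0.1 × 15 / 0.5 = 3.0 J/cm².
- With the exact 8 mm circle: 0.1 × 15 / 0.503 = 2.98 J/cm².
- Energy per point is 0.1 × 15 = 1.5 J, whereas 4 J/cm² on 0.5 cm² needs 2.0 J.

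The stated 4 J/cm² is not reproduced. The shortfall is 1 − 3/4 = 25%; the excess of the stated figure is 4/3 − 1 = 33%.

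**Step 3: can another reading give 4 J/cm²?**
- *Rounding of power, spot and time.* With 95–105 mW, 0.45–0.55 cm² and 14.5–15.5 s, the range runs from 0.095 × 14.5 / 0.55 = 2.5 to 0.105 × 15.5 / 0.45 = 3.6 J/cm².
- *Rounding of power density.* Even if 0.2 stood for 0.25 W/cm² and 15 s for 15.5 s, the result is 0.25 × 15.5 = 3.9 J/cm². That extreme would also contradict the stated power and spot.
- *Gaussian on-axis peak.* It depends on how the 8 mm diameter is defined: 2 × 3 = 6 J/cm² if it is the 1/e² diameter, 3 J/cm² if it is the 1/e diameter, and ln 2 × 3 = 2.1 J/cm² if it is the full width at half maximum. None is 4.
- *Distance of 1 mm.* Any beam spread enlarges the spot and lowers the fluence, which widens the gap.
- *Cumulative dose.* Two sessions give 2 × 3 = 6 J/cm², not 4.

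**Step 4: what 4 J/cm² would need, changing one input at a time.**

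| Change | Value needed | Value stated |
|---|---|---|
| Exposure time | 4 / 0.2 = 20 s | 15 s |
| Power density | 4 / 15 = 0.267 W/cm² (about 133 mW on 0.5 cm²) | 0.2 W/cm² (100 mW) |
| Spot area | 1.5 / 4 = 0.375 cm² (about 6.9 mm diameter) | 0.5 cm² (8 mm) |

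**Step 5: over a full course.** A point treated in all 8 sessions receives 8 × 3 = 24 J/cm² under the settings, against 8 × 4 = 32 J/cm² under the stated fluence.

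For comparison, the Er:YAG figures in Group 2 do agree: 80 mJ × 10 Hz = 0.8 W.

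**The case against.** The strongest reply accepts the arithmetic and disputes the consequences. Power, spot, power density and time fully define what the device delivers, and only the derived figure disagrees. A team that always uses 100 mW for 15 s gives one consistent dose, and a reader given all the settings can recompute 3 J/cm². Randomisation is untouched, and no sample size or endpoint rests on the fluence. The protocol does not say whether the device is set by time or by fluence, or how many operators there are, so mixed dosing is possible but not shown. Nothing in the protocol shows that 3 rather than 4 J/cm² changes efficacy or safety. The 24 against 32 J/cm² is the same 25% again, and it applies only to points treated at every one of the 8 sessions.

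Much of this is fair. The inconsistency does not bias the randomised comparison of the regimens actually given, its clinical weight is unknown, and the cumulative figure adds no separate harm. What the reply does not remove is the contradiction. It assumes that 15 s is right and 4 J/cm² is the slip, but the document supports the opposite reading equally well: 4 J/cm² may be the intended dose and 15 s a mistake for 20 s. Until that is settled, the protocol does not say what dose Group 1 should receive.

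**Conclusion.** The concern holds. As written, the Group 1 settings deliver 3.0 J/cm² (2.98 with the exact 8 mm circle), 25% below the stated 4 J/cm². This takes the beam as continuous and each point as exposed once per session, which is how the protocol reads.

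Because the optical figures agree among themselves, the error most likely lies in the exposure time or the fluence; the document does not show which. The point is limited to the PBM arm and to how its dose is specified. It makes no claim that 3 J/cm² is ineffective or unsafe. It still has to be put right before treatment starts, because the dose of a randomised arm must have a single value.

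**What to change.** The investigator should establish which figure was intended and correct the Group 1 list so that fluence = power × time / area. With the stated optics left alone, there are two ways to do this:

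- keep 15 s per point and state 3 J/cm² (1.5 J per point); or
- keep 4 J/cm² and set 20 s per point (2.0 J per point).

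Changing the power or the spot is also possible, but it would mean altering figures that now agree. The same corrected set should appear in the protocol, the case report form and the final report. If any patient has already been treated, the time per point actually used should be verified and recorded.

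The cost is a one-line protocol correction, with no extra patients or visits. If 20 s is chosen, each point takes 5 s longer.

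### Symptom improvement N divides by a baseline score that may be 0, so it has no value for some eligible patients and is unstable for worsening from low baselines

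*Protocol*

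**What the plan says.** Section I of the protocol lists "Reduction of pain intensity" as the second focus of the study. Section III, under Subjective Assessments, names two scales: "Pain: Visual Analogue Scale (0 to 10") and "Swelling or discomfort: numeric scale (0 to 10"). Symptom Improvement (N) is then defined by a formula that begins "N = [(baseline score - post treatment score", divided by the baseline score and expressed as a percentage.

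The disease criterion for entry in Section II is "Histopathological confirmation of erosive or ulcerative OLP". The other four inclusion criteria concern age, infection, recent treatment and consent. No inclusion or exclusion criterion sets a minimum pain or swelling/discomfort score. The rationale describes the disease as "often associated with pain and impaired function, especially in the erosive variant", which is frequent but not universal.

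The protocol gives no rule for a baseline of 0, no lower limit for N and no other measure of symptom improvement. It does not say whether the arms are to be compared on N.

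**The concern.** Because 0 is a permitted score and a symptom-free patient is eligible, the formula has no value for part of the population that the protocol admits. The two scales are separate, so a patient with pain may still score 0 for swelling or discomfort.

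For patients just above 0 the measure exists but behaves badly: a small absolute worsening becomes a very large negative percentage, with no matching gain on the positive side. If arms are compared on N as defined, patients at 0 drop out and the least symptomatic of the rest have the most leverage on arm means.

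Onset from 0 is foreseeable. Section VI says "Risks may include redness, swelling, pain, burning sensation, or changes in pigmentation", yet N, the only symptom-improvement measure defined, cannot register new pain or swelling in a patient who began at 0.

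**Working it through.** **Inputs from the protocol.** N = (b - p) / b × 100, where b is the baseline and p the post-treatment score; both lie between 0 and 10. Sixty patients in three equal groups give 60 / 3 = 20 per arm. The protocol states no figure for N that could be reproduced.

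**Domain.** At b = 0 the formula gives 0/0 for a patient who stays at 0 and -3/0 for one who goes to 3. Neither has a value.

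**Range.** The best case is p = 0, which gives +100% at every b above 0. The worst case is p = 10, which gives (b - 10) / b × 100: -900% at b = 1, -400% at b = 2, -100% at b = 5 and 0% at b = 10.

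**Same change, different N.** Take a 3-point worsening in one patient in an arm of 20, the other 19 averaging +60% (assumed). The arm mean is (19 × 60 + N) / 20.

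| Change | N | Arm mean |
|---|---|---|
| 1 to 4 | -300% | (1140 - 300) / 20 = 42% |
| 2 to 5 | -150% | (1140 - 150) / 20 = 49.5% |
| 5 to 8 | -60% | (1140 - 60) / 20 = 54% |
| 7 to 10 | -42.9% | (1140 - 42.9) / 20 = 54.9% |

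Against a mean of 60%, the loss is 18 points in the first row and 5.1 in the last. The only difference is where the patient started. A median would hardly move.

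**How many patients at 0.** The protocol gives no baseline distribution. Assume a normal latent score recorded in whole points, so that the share at 0 is Φ((0.5 - mean) / SD).

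| Assumed mean / SD | Share at 0 | Expected among 60 |
|---|---|---|
| 6 / 2 | 0.3% | 0.2 |
| 5 / 2.5 | 3.6% | 2.2 |
| 4 / 2.5 | 8.1% | 4.8 |
| 3 / 2.5 | 15.9% | 9.5 |

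If the true share were only 2%, the chance of at least one such patient among 60 is 1 - 0.98^60 = 70%; at 5% it is 95%.

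**Power.** This was examined because it bears on the remedy. Each scenario used 4,000 simulated trials of 20 against 20, two-sided alpha 0.05, with scores rounded and clipped to 0–10 and patients at baseline 0 dropped for N only. Entries are power in percent for the t-test on N / rank test on N / ANCOVA on all patients. Repeat runs agree to within about 3 points.

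| Baseline mean / SD | Additive effect | Proportional effect |
|---|---|---|
| 6 / 2 | 76 / 79 / 84 | 84 / 82 / 80 |
| 5 / 2.5 | 66 / 76 / 84 | 82 / 80 / 78 |
| 4 / 2.5 | 63 / 73 / 84 | 77 / 75 / 73 |
| 3 / 2.5 | 58 / 67 / 82 | 71 / 69 / 67 |

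Additive: post-treatment score at half of baseline, 1.5 points higher in one arm, SD 1.5. Proportional: post-treatment score at 60% against 30% of baseline, SD 30% of baseline. The ordering reverses between the two models, so power does not decide the matter.

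**The case against.** The algebra is not in dispute; the case against concerns its consequences.

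- **N is not named as the test variable, and the leverage example needs arm means.** True. The test, the summary statistic and a rule for zeros could all sit in a statistical analysis plan that is not at hand. But the protocol itself fixes the formula without a domain, so the defect is in its text. A median limits the leverage but gives no value to patients at 0.
- **The raw scores still record new symptoms.** True. The data are intact and only the derived measure fails. The protocol does not say that N is used to monitor harms.
- **Dropping patients at 0 does not bias the comparison.** This stands. Baseline precedes treatment, so the exclusion restricts the population rather than distorting the contrast between arms. Percent reduction among symptomatic patients is defensible for an aim of reducing pain. What is lost is some randomised patients and all information on onset.
- **Zeros may be rare for pain.** This stands in part. Only erosive or ulcerative disease is enrolled. If the VAS is read to 0.1, the same four assumptions give about 0.1%, 2.4%, 5.7% and 11.9%. A finer scale, however, also admits baselines below 1, where N is less stable still: a 2-point worsening from 0.5 gives -400%. The argument is weaker for swelling or discomfort, where a 0 is plausible even in a patient with pain.

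**Conclusion.** The concern holds. As written, N has no value for eligible patients at baseline 0 and gives lopsided values at low baselines. That much follows from the formula, the scale ranges and the entry criteria, without further assumption.

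The practical size is uncertain. The number without N could be anywhere from almost none to about 9.5 of 60, depending on assumed baseline distributions. The 18-point shift in an arm mean applies only if means of N are reported and a patient worsens from a baseline of 1. The instability at baselines of 1 or 2 does not depend on there being any zeros.

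This should be corrected, but it is not fatal, because the underlying scores are collected.

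**What to change.** State that arms are compared on the post-treatment 0–10 pain and swelling/discomfort scores, with the baseline score as covariate, in all randomised patients including those at 0. This can be an ANCOVA at a stated visit, or a repeated-measures model over the three post-treatment visits, the first of which is "One week after final session or cessation of steroid application". Keep N as a descriptive figure for patients with a baseline above 0, reported as a median together with the number per arm who have no N.

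The change is wording only: the scores are already collected, and no visits or patients are added. There are two small costs. The effect is reported in points rather than percent. If both the treatment effect and the noise are proportional to baseline, power may be about 4 points lower than with a t-test on N (for example 80% against 84%).
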